After data are exported from REDCap, we will perform data cleaning and run descriptives on all variables. We will analyze pre and posttest differences on knowledge, HBM constructs, self-efficacy and intentions using paired t-tests. Reliability analyses will be run for scales. Differences in HBM constructs, knowledge, PAM activation, and self-efficacy to manage cancer care and demographic or cancer history will be assessed by ANOVAs or independent t-tests to test moderator effects. Power was calculated using a paired t-test with an assumed standard deviation of paired difference of 4.0 points using a 0.05 level of significance and a medium correlation between pre- and post-test.

VII. References

DeSantis, C.E., et al., *Cancer treatment and survivorship statistics, 2014*. CA Cancer J Clin, 2014. **64**(4): p. 252-71.

Mertens, A.C., et al., *Cause-specific late mortality among 5-year survivors of childhood cancer: the Childhood Cancer Survivor Study*. J Natl Cancer Inst, 2008. **100**(19): p. 1368-79.

Group, C.s.O., *Long-term follow-up guidelines for survivors of childhood, adolescent and young adult cancers*, 2008, Children's Oncology Group: Arcadia, CA.

Klosky, J.L., et al., *Factors influencing long-term follow-up clinic attendance among survivors of childhood cancer*. Journal of Cancer Survivorship, 2008. **2**(4): p. 225-32.

Barakat, L.P., et al., *Factors that contribute to post-treatment follow-up care for survivors of childhood cancer*. Journal of Cancer Survivorship, 2012. **6**(2): p. 155-162.

Oeffinger, K.C., *Longitudinal risk-based health care for adult survivors of childhood cancer*. Current Problems in Cancer, 2003. **27**(3): p. 143-167.

Eshelman-Kent, D., et al., *Cancer survivorship practices, services, and delivery: a report from the Children's Oncology Group (COG) nursing discipline, adolescent/young adult, and late effects committees*. Journal of Cancer Survivorship, 2011. **5**(4): p. 345-357.

Oeffinger, K.C. and W.H. Wallace, *Barriers to follow-up care of survivors in the United States and the United Kingdom*. Pediatr Blood Cancer, 2006. **46**(2): p. 135-42.

Patenaude, A.F. and M.J. Kupst, *Psychosocial functioning in pediatric cancer*. Journal of Pediatric Psychology, 2005. **30**(1): p. 9-27.

Heirs, M., et al., *A systematic review of models of care for the follow-up of childhood cancer survivors*. Pediatric Blood & Cancer, 2013. **60**(3): p. 351-356.

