This is a mixed methods study involving cohorts of 18-25 year old childhood cancer survivors and/or their parents to determine predictors of transition readiness among those engaged in pediatric survivor care (Aim 1), predictors of adherence to adult survivor-focused healthcare among those who have transferred out of pediatrics (Aim 2), and optimize content, format, and delivery of electronic educational media to increase knowledge about and motivation for survivor care among AYA survivors (Aims 3 & 4). Through our design and methods, we are seeking to clarify what are the most salient social-ecological risk and resilience factors that should serve as targets for interventions, as well as what patterns exist among co-occurring risk factors that maximize patients' risk for poor transition outcomes. The planned approach to accomplish our specific aims will employ both quantitative and qualitative methods to test the following hypotheses:

Aim 1 Hypotheses:

- *A1 Hypothesis 1:* AYA healthcare responsibility, survivor health beliefs, and developmental maturity will be significantly related to increased perceptions of transition readiness.

- *A1 Hypothesis 2:* AYA psychosocial distress, poorer neurocognitive functioning, and deprived neighborhood-level social determinants will be significantly related to decreased perceptions of transition readiness.
- *A1 Hypothesis 3:* The relationship between parental involvement in survivor healthcare and perceptions of transition readiness will be mediated by AYA healthcare responsibility.
- *A1 Hypothesis 4:* When individual transition readiness risk factors are included in principal component analyses (PCA), 2 or more components will emerge indicating subgroups at risk for poor transition outcomes.

Aim 2 Hypotheses:

- *A2 Hypothesis 1:* Survivor health beliefs, developmental maturity, and healthcare responsibility will predict adherence to adult survivor care.
- *A2 Hypothesis 2:* Parental involvement in survivor healthcare will predict adherence to survivor care; this relationship will be stronger for survivors with higher psychosocial distress, as well as lower levels of developmental maturity and neurocognitive functioning.
- *A2 Hypothesis 3:* Access to care problems (e.g., geographical distance, insurance) and lower patient satisfaction will negatively predict adherence to initial survivor care.

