The primary goals of this study are to determine characteristics that influence or predict transition readiness and transition to adult survivor care. Because there are many candidate predictors and overlap between variables with respective substantive meaning, predictors are likely to be highly correlated (i.e., neurocognition and developmental maturity). Therefore, we propose a three-step modeling process to identify general groups or constructs associated with the outcomes of interest. First, in a univariate analysis setting, we will investigate the relationship between each potential predictor and the continuous outcome transition readiness using simple linear regression and correlation analysis. Similarly, we will use Chi-square tests and/or logistic regression to identify factors associated with the binary outcome successful transition (yes/no). Due to the high

correlation/overlap with some of the potential predictors, principal component analysis (PCA) will be performed using those variables significant at the 0.1 level from step 1. The number of components retained in the model will be determined by eigenvalues and percent-variance explained. Finally, based on the results of the PCA, composite variables (which will contain multiple predictors) will be created by standardizing (convert to a z-score) each predictor variable and taking the mean value of the standardized predictor variables that uniquely load on a given component. We will examine the effect of each composite variable on the outcome transition readiness using linear regression and the outcome successful transition using logistic regression. All statistical analyses will be performed using SAS.

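### No model in the Aims 1 and 2 analysis can test the mediation hypothesis (A1 Hypothesis 3) or the moderation clause of A2 Hypothesis 2

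*Combined protocol and SAP*

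**What the plan says.** Section III (Study Design) lists the hypotheses as ones that the planned approach will test. Two go beyond simple association:

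- A1 Hypothesis 3: "The relationship between parental involvement in survivor healthcare and perceptions of transition readiness will be mediated by AYA healthcare responsibility".
- A2 Hypothesis 2 has two clauses. The first is a main effect: "Parental involvement in survivor healthcare will predict adherence to survivor care". The second is effect modification: "this relationship will be stronger for survivors with higher psychosocial distress, as well as lower levels of developmental maturity and neurocognitive functioning".

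Section VI (Statistical Analysis Plan, Aims 1 & 2) gives one three-step process for both aims.

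- Step 1, for readiness: "we will investigate the relationship between each potential predictor and the continuous outcome transition readiness using simple linear regression and correlation analysis". For the yes/no adherence outcome, Chi-square tests and/or logistic regression are used in the same univariate setting.
- Step 2: PCA, "performed using those variables significant at the 0.1 level from step 1".
- Step 3: composites are formed by "taking the mean value of the standardized predictor variables that uniquely load on a given component", and then "We will examine the effect of each composite variable on the outcome transition readiness using linear regression and the outcome successful transition using logistic regression".

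The Aims 1 and 2 power statement covers univariate correlations and odds ratios only. Moderator effects are mentioned once in section VI, among the Aim 4 pre-test/post-test analyses. The reference list includes a review of structural equation modelling, but section VI does not use that method.

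**The concern.** Mediation needs at least two fitted relations: involvement to responsibility, and responsibility to readiness with involvement held fixed. Moderation needs a product term, or a comparison of the involvement effect across levels of the moderator. The three steps supply neither. They suit the component hypotheses (A1 Hypothesis 4 and A2 Hypothesis 4), but two other stated claims are left without an estimate.

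The study wants to know how parents figure in transition and whom to target with interventions, and these are the two hypotheses that address that most directly. If the models are not written down, either the hypotheses go unanswered, or someone chooses the mediator model, the reporter and the moderator scores after seeing the data.

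**Working it through.** **1. Hypotheses against steps.**

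- *Involvement to responsibility (A1 Hypothesis 3).* Step 1 relates each predictor to the outcome, never one predictor to another. Step 3 regresses the outcome on composites. No step fits this path.
- *Responsibility to readiness, adjusted for involvement (A1 Hypothesis 3).* Step 1 has one predictor per model, so its coefficients are total associations. Step 3 uses composites, not the two scores. Not fitted.
- *Involvement predicts adherence (A2 Hypothesis 2, first clause).* Tested in step 1.
- *Involvement by distress, maturity or neurocognition (A2 Hypothesis 2, second clause).* No product term and no stratification in any step. The 0.1 screen also acts on marginal association, so a moderator that changes the involvement effect but has little association of its own with adherence can be dropped.

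**2. The plan's own power figure.** It states at least 80% power for correlations of 0.25 or more. Using Fisher's z with two-sided alpha 0.05 (assumed, because section VI states 0.05 only for Aim 4), power = Φ(atanh(0.25) × √(n − 3) − 1.96). This gives 78.9% at n = 120, 87.2% at n = 150 (75% of the 200 stated as eligible for Aim 1) and 96.4% at n = 220 (the Aim 1 figure printed). The correlation claim is in effect reproduced, but it is a one-predictor figure and says nothing about an indirect effect or an interaction.

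**3. If exposure and mediator share a component.** Let X be involvement and M responsibility, both standardised and coded in the same direction, with correlation 0.5 (assumed). The composite is C = (X + M)/2, with variance (2 + 2 × 0.5)/4 = 0.75.

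- Full mediation (effect of M on readiness 0.4, no direct effect of X): cov(X,Y) = 0.5 × 0.4 = 0.2 and cov(M,Y) = 0.4, so cov(C,Y) = 0.3.
- No mediation (direct effect of X 0.4, none of M): cov(X,Y) = 0.4 and cov(M,Y) = 0.2, so again cov(C,Y) = 0.3.

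In both cases the slope is 0.3/0.75 = 0.40 and the correlation is 0.3/√0.75 = 0.35. Simulation gave the same values. The composite regression cannot tell the two apart.

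**4. If they are also inversely related and not sign-aligned.** corr(C,Y) = [(r_AR,Y + r_PI,Y)/2] / √[(2 + 2 r_AR,PI)/4], where AR is adolescent responsibility and PI parent involvement. All inputs are assumed; the documents report no such correlations.

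- r_AR,PI = -0.5, r_AR,Y = +0.4, r_PI,Y = -0.3: 0.05/0.5 = 0.10.
- Same outcome correlations, r_AR,PI = -0.3: 0.05/0.592 = 0.08. With r_AR,PI = -0.7: 0.05/0.387 = 0.13.
- r_PI,Y = -0.1, the rest as in the first case: 0.15/0.5 = 0.30.
- First case with PI reverse-scored: 0.35/√0.75 = 0.40.

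**5. What the missing models could deliver.** The effect sizes are assumptions, because the plan gives none for either hypothesis.

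*Mediation:* joint significance of both paths, equal standardised paths, no direct effect, 4,000 simulations.

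| Each path | N = 150 | N = 220 |
|---|---|---|
| 0.14 | 16% | 30% |
| 0.20 | 47% | 70% |
| 0.25 | 75% | 92% |
| 0.30 | 91% | 98% |

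*Interaction:* N = 120 with 20 to 30% adherent is 24 to 36 events. For balanced binary involvement and moderator (30 per cell), power = Φ(log(ROR)/√v − 1.96), where ROR is the ratio of odds ratios and v the sum over four cells of 1/(30 q(1 − q)), with q the cell's adherence rate. With ROR = 2.5 and 20% adherent overall, three cells have q ≈ 0.16 and one q ≈ 0.32, so √v ≈ 0.95 and power is Φ(0.916/0.948 − 1.96) = 16%. Across 20 to 30% adherence and two baseline odds ratios (1 and 1.5) the range is 15 to 20%. About 752 (30% adherent) to 1,012 (20% adherent) patients would be needed for 80%. With continuous scores and 25% adherent, simulated power is about 43% for an interaction odds ratio of 1.5 per SD-by-SD and 82% for 2.0. It falls to 33% and 74% when main effects of 0.4 log-odds per SD are added.

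**The case against.** The strongest reply is that this is an omission of detail in a largely exploratory plan. Every variable is collected and nothing forbids an extra model. Step 1 also still reports involvement and responsibility separately, whatever later happens to the composites. That is right as far as it goes: the data can support the tests, and any cancellation is confined to step 3. But step 1 cannot stand in for either missing model.

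Two stronger readings are tempting, and the documents do not support them.

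- A reader might infer that both hypotheses go wholly untested. The main-effect clause of A2 Hypothesis 2 is tested in step 1; only its moderation clause is not.
- A reader might infer that the composite rule necessarily destroys the mediation contrast. That requires both scores to pass the 0.1 screen and load uniquely on the same component; cancellation further requires that they be inversely related and averaged without reverse-scoring. The documents give no correlation or loading for these scores. Section VI states no sign rule but does not rule one out, and the talk of entering risk factors in A1 Hypothesis 4 may imply common-direction coding.

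It is also fair to object that the interaction models will say little at N = 120. The 82% figure needs the involvement odds ratio to change fourfold (2.0 squared) between one SD below and one SD above the moderator mean. That limits what can be claimed from the models; it does not excuse leaving them unspecified.

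**Conclusion.** The point stands in this form: the three-step analysis contains no model that can test A1 Hypothesis 3 or the moderation clause of A2 Hypothesis 2. This follows from the text alone and depends on no assumed number. If involvement and responsibility fall on different components, the models are still absent.

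The merging of exposure and mediator, and the drop to a correlation of 0.10, are a conditional risk. The arithmetic is correct, but it rests on assumed correlations and loadings.

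The plan should be amended. The mediation test would be reasonably powered for paths of about 0.25 to 0.30 (75 to 91% at N = 150, 92 to 98% at N = 220) and weak below 0.20. The interaction tests would be imprecise under most plausible effects.

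**What to change.** Add the following to section VI, outside the PCA steps and fitted whatever the 0.1 screen shows, keeping the involvement and responsibility scores separate.

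1. *A1 Hypothesis 3.* Regress RTQ-AR on RTQ-PI, and RTQ-Overall on RTQ-PI plus RTQ-AR. Report the indirect effect with a percentile-bootstrap 95% CI. Name the reporter, since readiness is scored by both patient and parent (section III.A). Describe the result as cross-sectional statistical mediation; section II calls the design cross-sectional, so temporal order is not shown.
2. *A2 Hypothesis 2, moderation clause.* Fit a logistic regression of adherence on centred RTQ-PI, one moderator (distress, maturity or neurocognition) and their product, one moderator at a time. Name a single score for each moderator, because Table 2 lists several instruments per construct. Report interaction odds ratios with CIs, state that they are imprecise at N = 120, and either adjust for the three tests (for example 0.05/3 = 0.017 each) or label them exploratory.
3. *Composites.* State a sign-alignment rule before z-scores are averaged.

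The cost is SAP wording and a few extra models on scores already in Table 2, with no new data collection. The downside is wide intervals for the interactions, which must be reported as such.

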No biological specimens will be collected as part of this research. Participants' electronic medical records will be reviewed to abstract treatment data. Confidentiality within this study will be rigidly maintained. Computer files will use study identification numbers only and are password protected. Only necessary personnel will have access to any of these files. Based on existing best practices for security and privacy in health information technology, we will identify the technologies and features to be employed to ensure privacy and security of personal information. This will address identity and access management, secure storage, secure messaging, encryption, and other security technologies and approaches.

VI. Statistical Analysis Plan

Aims 1 & 2: In 2015, the Aflac Cancer Survivor Program (Aflac CSP) saw over 200 AYA survivors aged 18-22 years (Aim 1). Additionally, the Aflac CSP has transitioned approximately N=165 survivor patients since 2013 (Aim 2). Based on our previous research with survivor patients > 18 years of age, we estimate that less than 2% of AYAs will be non-English speakers. During the year-long study period, we anticipate that there will be at least N=200 AYA patients who are eligible for participation in Aim 1 and at least N=160 AYA patients who are eligible for participation in Aim 2. Previous studies with our AYA population have yielded initial recruitment rates and retention rates above 80%. Of the eligible AYA patients, we estimate that 75% [Aim 1: N=220 patient-parent dyads (440 participants), Aim 2: N=120 patient-parent dyads (240 participants), Aim 3: N= 20 patients, Aim 4: N=58] will participate in each aim of the study. In our univariate analysis, these sample sizes provide us with at least 80% or greater power to detect correlations of magnitude ≥ 0.25 and odds ratios of at least 2.5, depending on the prevalence of the risk factor, assuming that approximately 20-30% of patients meet our definition of successful transition. Power analyses were conducted using PASS v. 11 (Kaysville, UT) using a two-sided test for a single correlation and a two sample Z-test for proportions. Given these anticipated numbers, we can assess at most 15 possible predictors for aim 1 and 12 predictors for aim 2 to ensure that we have at least 10 observations per predictor in our principal component analysis.

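### Hypothesis 4 of Aims 1 and 2 rests on a component count that is a weak test, and a principal component cannot show that at-risk subgroups of survivors exist

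*Combined protocol and SAP*

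**What the plan says.** Section III (Study Design) lists A1 Hypothesis 4 and A2 Hypothesis 4 among the hypotheses to be tested. Both predict, in the same words, that "2 or more components will emerge indicating subgroups at risk for poor transition outcomes" once the individual risk factors enter a principal component analysis (PCA).

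Section VI (Statistical Analysis Plan, Aims 1 & 2) sets out three steps:

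1. Each predictor is related to the outcome on its own.
2. Then "principal component analysis (PCA) will be performed using those variables significant at the 0.1 level from step 1". On retention, the plan says only: "The number of components retained in the model will be determined by eigenvalues and percent-variance explained".
3. Predictors that load uniquely on one component are standardised and averaged into a composite. Each composite is then regressed on transition readiness (Aim 1) or successful transition (Aim 2).

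The same section caps the analysis at "at most 15 possible predictors for aim 1 and 12 predictors for aim 2 to ensure that we have at least 10 observations per predictor". It also says that "predictors are likely to be highly correlated". Section II states as an objective that the study will clarify which survivors are most at risk and should be recruited to later interventions.

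**The concern.** A hypothesis judged on a count needs a rule under which the count can come out too low when no second dimension exists. The plan names two retention criteria but gives no threshold for either, no order of precedence and no comparison with what random data would produce. Common versions of both criteria tend to return several components whether or not several dimensions exist.

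The second difficulty does not depend on the cutoff. A component is a weighted combination of variables. Two components say that the predictors fall into two sets; they do not say that there are two kinds of survivor. A confirmed Hypothesis 4 could nevertheless be reported as evidence of at-risk subgroups and influence who is approached for later interventions.

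**Working it through.** **Inputs from Section VI.** The only stated figure that bears on the PCA is the cap on predictors, at 10 observations each.
- Aim 2: 75% × 160 eligible = 120, and 120/10 = 12. This reproduces the cap.
- Aim 1: 75% × 200 eligible = 150, and 150/10 = 15. This reproduces the cap. The printed 220 dyads would give 220/10 = 22, so the cap of 15 rests on 150.

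Both Aim 1 sizes are carried below.

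**Assumptions, because the plan gives no values.** Retention at eigenvalue above 1; alternatively, enough components to reach 70% cumulative variance. Data are normal. One-factor data have equal loadings, so the correlation between any two variables is r = loading².

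**Unrelated variables, eigenvalue above 1.** The eigenvalues of a correlation matrix of p variables sum to p, so they average 1, and sampling error puts roughly half of them above 1. Share of simulated data sets with two or more components (N=120 to 220):

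| Variables in the PCA | Two or more components |
|---|---|
| 2 | 0% |
| 3 | about 48% |
| 4 | about 93% |
| 5 | over 99% |
| 6 or more | 100% |

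The mean number retained is 7.1 with 15 variables (N=150) and 5.7 with 12 (N=120).

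**One true factor, eigenvalue above 1.** The correct answer here is one component. All eigenvalues after the first equal 1−r in the population, and sampling error lifts the second above 1 when r is small.

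| Loading (r) | N=120, 12 variables | N=150, 15 variables | N=220, 15 variables |
|---|---|---|---|
| 0.5 (0.25) | 98–99% | 100% | 97% |
| 0.6 (0.36) | 46% | 55% | 13% |
| 0.65 (0.42) | 9% | 10% | 0.3% |
| 0.7 (0.49) | 0.5% | 0.4% | 0% |

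Fewer variables lower the rate. At loading 0.5, 8 variables give 67% (N=120), 50% (N=150) and 21% (N=220); 6 variables give 29%, 16% and 3%.

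**One true factor, 70% variance.** The first component explains (1+(p−1)r)/p. With p=12 and r=0.49 this is (1+11×0.49)/12 = 6.39/12 = 0.53, short of 0.70. To reach 0.70, r must be at least (0.70×12−1)/11 = 7.4/11 = 0.67. In simulation this rule gave two or more components in all one-factor data sets with 8 to 15 variables, even at loading 0.7.

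**The step-1 screen.** If all predictors are unrelated to the outcome and to each other, about 1.5 of 15 or 1.2 of 12 pass p<0.1. Two or more components by eigenvalue above 1 then occur in about 11% of runs (Aim 1 sizes) and 7% (Aim 2, with an assumed 25% successful transition). If 40 candidates were screened (an assumed number, above the plan's cap), the figure would be about 65%.

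**Parallel analysis.** Retaining only components whose eigenvalue exceeds the 95th percentile from random data of the same N and number of variables gives two or more components from noise in 0.7% (N=150, 15 variables), 0.8% (N=220, 15) and 0.5% (N=120, 12). In the one-factor settings it gives at most 1%.

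**People or variables.** Set beside Hypothesis 4, the Section VI steps produce screened predictors, components, composites and regressions. None assigns a survivor to a group: there is no clustering, no latent class or profile analysis and no threshold on a score.

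**The case against.** A reader might infer that Hypothesis 4 cannot fail and that noise alone would confirm it. The documents do not support that.

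- The eigenvalue-above-1 cutoff is not in the plan; it is an assumption here.
- The plan expects high correlation among predictors. Under eigenvalue above 1, a single factor with loadings near 0.7 correctly returns one component in over 99% of data sets.
- The figures for unrelated variables describe variables already in the PCA. Under the plan's own screen and cap, a complete null confirms the hypothesis in only about 7 to 11% of runs.

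All of this stands. What remains is that, among the variables that pass, the count cannot reliably tell one dimension from several at moderate correlation. Where eigenvalue above 1 does return one component, a 70% variance target still points to two or more, and the plan does not say which criterion prevails.

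A reader might also infer that the study can no longer say who is at risk. That goes too far. Evidence on risk factors comes from the step-1 and step-3 models, which do not depend on Hypothesis 4, and Section II already speaks of patterns among risk factors. But Hypothesis 4 is not stated in terms of the step-3 result, and that regression does not identify groups of people.

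Parallel analysis is one acceptable rule among several. Stating any cutoff in advance would remove the discretion, but a cutoff of eigenvalue above 1 would leave the weakness shown above.

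**Conclusion.** The point holds in two parts.

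First, the count is a weak criterion. How weak depends on the unstated cutoff, on how many variables pass the screen and on their correlation. For a single true factor at the planned sizes, a wrong finding of two or more components ranges from 97–100% (loading 0.5) to under 1% (loading 0.7) with eigenvalue above 1, and is close to certain with a 70% variance target. Both cutoffs are assumptions.

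Second, and with no assumption, Hypothesis 4 cannot support a statement about subgroups of survivors, because the planned analysis groups predictors and never classifies people.

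The regressions are unaffected. The conclusion attached to Hypothesis 4 is what needs to change.

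**What to change.** 1. In Section VI, replace the retention sentence with parallel analysis: keep a component only if its eigenvalue exceeds the 95th percentile from random data with the same N and the same number of variables entered.
2. Judge Hypothesis 4 on that count together with the step-3 association of the composites with the outcome. Those predictors were already selected on the same outcome, so the step-3 p-values will be somewhat optimistic and should be reported with that caveat.
3. In A1 and A2 Hypothesis 4, replace the reference to subgroups at risk with sets of co-occurring risk factors, in line with the aims in Section II. If groups of survivors are really meant, a person-level method such as latent profile analysis would have to be specified in advance.

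Reporting the outcome by tertile of composite score is optional description; it would not show that subgroups exist.

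The cost is SAP wording and a few lines of code, with no new data. The downside is that fewer components may be retained.
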